# LIST OF ABBREVIATIONS

Abbreviation	Explanation
AE	Adverse event
ANCOVA	Analysis of Covariance
ATC	Anatomical-Therapeutic-Chemical
ATS/ERS	American Thoracic Society/ European Respiratory Society
BDRM	Blinded Data Review Meeting
BMI	Body Mass Index
ECG	Electrocardiogram
eCRF	Electronic case report form
ENS	Enrolled Set
FDA	Food and Drug Administration
FEV 1	Forced expiratory volume in one second
FP	Fluticasone Propionate
FVC	Forced Vital Capacity
HFA	Hydrofluoroalkanes
IWRS	Interactive Web Response System
LOCF	Last Observation Carried Forward
LS	Least Squares
mcg	Microgram
MedDRA	Medical Dictionary for Regulatory Activities
mITT	Modified Intent-to-Treat
mL	milliliter
NAEPP-EPR3	National Asthma Education and Prevention Program Expert
	Panel Report 3
NHANES III	National Health and Nutrition Examination Survey III
PEF	Peak expiratory flow
PEFR	Peak expiratory flow rate
pMDI	Pressurized metered dose inhaler
PPS	Per-protocol Set
PT	Preferred term
RiN	Run-in Set
RS	Reference Standard
SAE	Serious Adverse Event
SAF	Safety Analysis Set
SAP	Statistical Analysis Plan
SOC	System organ class
TEAE	Treatment-emergent adverse event
USA	United States of America

#### 1. INTRODUCTION

The purpose of this statistical analysis plan (SAP) is to provide details of the statistical analyses that have been outlined within the protocol "A Randomized, Blinded, Parallel Group, Placebo-Controlled, Multiple Dose, Multicenter Study to Compare the Therapeutic Equivalence of Fluticasone Propionate Pressurized Metered Dose Inhaler, 110 mcg, to Flovent® HFA 110 mcg, in Adult Subjects with Asthma", amendment 2, dated June 10, 2019.

Teva Pharmaceuticals USA, Inc. is developing a new generic formulation of fluticasone propionate pressurized metered dose inhaler, 110 mcg for which demonstration of bioequivalence to the reference product (i.e., Flovent®) is required. This study is designed to evaluate the bioequivalence between the administered test and reference products in accordance with the recommendations outlined in the US Food and Drug Administration (FDA) Draft Guidance on Fluticasone Propionate (Oct., 2017, Rev. July, 2018).

#### 2. OBJECTIVES

# 2.1 Primary Objective

The primary objective of this study is to confirm the therapeutic equivalence of FP pMDI 110 mcg and the RS, Flovent HFA 110 mcg, after a 4 week (28 day \_\_\_\_\_\_\_) Treatment period in adult subjects with chronic but stable asthma as defined in the NAEPP-EPR3 guidelines at least 6 months prior to Enrollment at Screening Visit 1a.

# 2.2 Secondary Objective

[figure not shown]
The secondary objective of this study is to confirm the Test, FP pMDI 110 mcg, and RS, Flovent HFA 110 mcg, products are statistically superior to placebo (p< 0.05) on the primary study endpoint.

#### 3. STUDY OVERVIEW

### 3.1 Study Design

This is a multicenter, blinded, parallel group, placebo-controlled, randomized, multiple dose clinical study designed to confirm therapeutic equivalence of FP pMDI 110 mcg per actuation and Flovent HFA 110 mcg in adult subjects with asthma.

The Screening and Run-in study periods and visit windows described in this section may be extended with Sponsor approval. The Treatment period may not be extended.

The Screening period will have up to 2 visits. Screening Visit 1a may be conducted up to 28 days prior to Visit 1b. At Visit 1a subjects will provide written informed consent, demographics, medical history, and concomitant medication information. Subjects will receive rescue medication for the duration of the study. Subjects' height and weight will be measured and BMI will be calculated. Subjects must withhold rescue medication for 6 hours prior to performing any spirometry. If all protocol-defined washout requirements are met, Visit 1a and 1b may be combined and conducted on the same day.

At Screening Visit 1b, subjects will perform Screening spirometry with reversibility. Prebronchodilator FEV1 must be  $\geq$ 45% and  $\leq$ 85% of predicted normal value at Screening Visit 1b using NHANES III predicted values. For Screening Visit 1b only, subjects who fail to meet FEV1  $\geq$ 45% and  $\leq$ 85% of predicted normal value may repeat the visit one time within 1 week. Subjects must demonstrate reversibility of airway obstruction  $\geq$ 12% and  $\geq$ 200 mL of FEV1 within 30 minutes of 360 mcg albuterol inhalation (4 puffs). Subjects who achieve  $\geq$ 10% but <12% or achieve  $\geq$ 12% but 175-199 mL reversibility at Screening Visit 1b may repeat the visit one time within 1 week. Subjects may have only one repeated visit during the Screening period.

Vital signs will be collected at all clinic visits after Screening Visit 1a (blood pressure and heart rate). Physical examination, urinalysis, drug/alcohol/cotinine screening, laboratory screening (blood: hematology, chemistry), and urine pregnancy test (women of childbearing potential only) will be conducted at Screening Visit 1b. A 12-lead ECG will be collected. Subjects must have no evidence or history of clinically significant disease such as congestive heart failure, myocardial infarction, or cardiac dysrhythmia.

At the end of the Run-in period subjects will be randomized to treatment if they continue to meet all general Inclusion/Exclusion criteria. In addition, they must meet all randomization inclusion criteria and no randomization exclusion criteria specified in the protocol.

Eligible, randomized subjects will receive the first dose of study medication following serial spirometry at Visit 2 Randomization. Subjects will receive blinded study medication with instructions for home for the minimum 28 day () Treatment period. Subjects will be instructed to take two oral inhalations twice daily, with a dosing interval of approximately 12 hours.

Subjects will review eDiary requirements and instructions for use of diary at home, and will complete the first diary entries at the clinic under site staff supervision. Subjects will be instructed to record eDiary twice-daily (morning and evening) entries for study drug dosing and peak flows. Once-daily (morning) entries for rescue medication use, asthma symptoms, and reporting health and medication changes will also be recorded. Subjects will be instructed to withhold their morning medication (last dose should be approximately 12 hours prior to lung function tests), as well as rescue medication for 6 hours, on the day of Visit 3 Day 29.

[figure not shown]
Medication and eDiary compliance will be monitored throughout the Run-in and Treatment period, beginning when the eDiary/PEF device is dispensed. Compliance monitoring will include alerts, edit checks, and data management review. Sites will contact subjects as needed to follow-up on diary and medication compliance alerts.

Subjects will return to the clinic for Visit 3 Day 29 at the end of the minimum 28 day

Treatment period. The subject's interim medical history (including AEs) and required medication washout will be reviewed. Washout for Treatment medication must be observed for a minimum of 6 hours on Visit 3 Day 29. Subject must withhold rescue medication for 6 hours prior to spirometry on the day of Visit 3 Day 29. Laboratory screening (blood: hematology, chemistry) will be conducted. Urine pregnancy tests will be conducted for women of childbearing potential. The subject's Diary and medication compliance will be reviewed.

Subjects will perform serial spirometry over approximately 60 minutes, subjects will be required to perform three separate sessions of spirometry, allowing adequate time for subject

recovery between sessions.  1. Sites will
collect any remaining study medication and the eDiary device. Subjects will be discharged from the study after confirmation of stability by the Investigator.
If subjects decide to withdraw from the study prior to Visit 3 Day 29, an Early Termination visit will be scheduled, if possible. The subject's interim medical history (including AEs) and concomitant medications will be reviewed. Laboratory screening (blood: hematology, chemistry) will be conducted. Urine pregnancy tests will be conducted for women of childbearing potential. The subject's Diary and medication compliance will be reviewed. The remaining study medication and the eDiary device will be collected. A single spirometry session may be conducted if deemed necessary by the Investigator. Subjects will be discharged from the study after the Early Termination Visit upon confirmation of stability by the Investigator.
A detailed Schedule of Procedures is provided in Appendix 11.1.
3.2 Sample Size

of an SAE, the Investigator may un-blind the subject's drug assignment when necessary to make treatment decisions for the subject. The Sponsor should be notified of the event prior to breaking the code, if possible. If this is not possible, the Sponsor should be notified immediately afterwards, and the subject's drug code assignment should not be revealed to the Sponsor. The circumstances leading to the breaking of the code should be fully documented in the Investigator's study files and in the subject's source documentation. The subject's treatment assignment should not be recorded in any study documents.

Unless emergency unblinding occurs, treatment group assignment will be kept blinding until the final database lock.

### 4. STUDY ENDPOINTS/OUTCOMES

This study's primary efficacy endpoint is mean change in morning pre-dose FEV1 from the time of treatment randomization to Week 4 (Day 29 \_\_\_\_\_).

#### 5. HYPOTHESES TESTING

# **Hypothesis of Equivalence**

A two-sided, 90% confidence interval on the test/reference ratio for the primary endpoint will be constructed using an Analysis of Covariance (ANCOVA) model of the Test and Reference results with

Bioequivalence will be established if the 90% confidence interval for the ratio of test/reference means is contained within the interval [80.00%, 125.00%] for the Per-protocol Set.

# **Hypothesis of Superiority**

In order to demonstrate adequate sensitivity, both test and reference treatments will be compared with placebo with respect to the primary endpoint using an ANCOVA model

Both treatments must be statistically superior to placebo for the Modified Intent-to-Treat Set in order to validate the assessment of clinical endpoint bioequivalence for the test/reference ratios for the primary endpoint.

#### 6. ANALYSIS SUBSETS

### 6.1 Enrolled Set (ENS)

The Enrolled Set (ENS) will consist of all subjects who provided informed consent.

#### 6.2 Run-in Set (RiN)

All patients who enter the Run-in Period and have a record of at least one study drug (placebo) administrationion the Run-in Period.

### 6.3 Run-in Failure Set (RIF)

The Run-in Failure Set will consists of all subjects in the Run-In set who did not receive any randomized study drug following randomization.

### 6.4 Randomized Set

The randomized set will consist of all subjects who were randomized.

# 6.5 Safety Analysis Set (SAF)

The Safety Analysis Set (SAF) will consist of all randomized subjects who received at least 1 dose of randomized study drug during the Treatment Period. Subjects will be classified by actual treatment received. The SAF will be the primary population for the safety analysis.

### 6.6 Modified Intent-to-Treat (mITT) Set

The Modified Intent-to-Treat (mITT) set will consist of all randomized subjects who rec	eivec
at least 1 dose of randomized study drug during the Treatment Period.	

Subjects will be classified by the treatment to which they were randomized. This population will be considered as definitive for testing superiority.

# 6.7 Per-protocol Set (PPS)

The Per-protocol Set (PS) will consist of all subjects in the mITT set who had between 75% and 125% compliance with the dosing schedule in the Treatment period, and had no major protocol deviations that are considered to have an impact on the analysis of the primary endpoint. The PPS will be defined before database lock and unblinding during the BDRM.

In the PPS subjects will be classified by randomized treatment. This population will be considered as definitive for testing bioequivalence.

#### 7. STATISTICAL METHODS OF ANALYSIS

# 7.1 General Principles

The statistical analyses will be performed by \_\_\_\_\_, with approval of the Sponsor, using SAS Version 9.4 (or higher). All tables, figures and listings will be produced in landscape format.

In general, all data will be listed by subject and visit/time point where appropriate. The summary tables will be stratified by, or have columns corresponding to, treatment groups.

The total number of subjects in the treatment group (N) under the specified analysis set will be displayed in the header of summary tables.

Data will be summarized using descriptive statistics for continuous variables. Unless otherwise specified, descriptive statistics will include number of subjects, mean, standard deviation, minimum, median and maximum. Number of subjects with missing values will also be displayed, but only if non-zero. The minimum and maximum statistics will be presented to the same number of decimal places as the original data. The mean and median will be presented to one more decimal place than the original data. The standard deviation will be presented to two more decimal places than the original data.

In summary tables of categorical variables, counts and percentages will be displayed. The count [n] indicates the actual number of subjects in a particular category, which should always be less than or equal to the total number of subjects in the respective study group with known (non-missing) category [M]. Percentage will be obtained by: % = n/M\*100. Unless otherwise specified, all percentages will be expressed to one decimal place.

All statistical tests will be two-sided at a significance level of  $\alpha = 0.05$ , unless otherwise indicated. No adjustment will be made for multiplicity.

Baseline will be defined as the last assessment, scheduled or not, prior to the first dose of the randomized study drug, unless otherwise specified.

In by-visit summaries, only data collected on scheduled visits/timepoints will be summarized. Data from unscheduled assessments will be included in listings and may be used in determination of baseline if applicable.

Relative days will be calculated relative to date of first dose of randomized study medication. Relative days will be calculated as follows only when the full assessment date is known (i.e., partial dates will have missing relative days).

For assessment on or after the day of first dose of the randomized study drug:

# 7.2 Subject Disposition

This analysis will be based on the ENS. The number of subjects enrolled in the study, randomized to treatment, included in the SAF, mITT, and PPS, prematurely discontinued from the study after randomization (along with the reasons for discontinuation) will be presented. The same analysis will be repeated by study site.

An overall summary of the number of subjects in each population by site will be created.

All disposition information will be listed. Additionally, a listing of subjects who discontinued from the study prematurely will be created, including date of discontinuation and primary reason. Also a listing of enrollment details will provide the date of informed consent/assent and inclusion/exclusion criteria not met, if any.

### 7.3 Demographic and Baseline Characteristics

Demographic and baseline characteristics will include:

- age
- sex
- race
- ethnicity
- baseline height, weight and body mass index (BMI)
- time since asthma diagnosis (years)

Descriptive statistics will be presented for continuous variables. Frequency counts and percentage will be presented for categorical variables. Height will be reported in centimeters, weight in kilograms and BMI in kg/m^2.

Age will be derived from

.

Demographic and baseline characteristics will be evaluated for comparability across treatment

groups in the following manner. Continuous variables will be analyzed with an analysis of variance with factors of treatment and investigational site. Overall p-value for the global null hypothesis of all groups being equal will be displayed.

These analyses will be performed for the SAF, mITT and PPS.

All demographic parameters and baseline characteristics will be presented in the by-subject listings.

# 7.4 Medical history

Medical history will be summarized by MedDRA (version 22.0) System Organ Class and Preferred Term. One subject will be counted once for each applicable Preferred Term and System Organ Class. This summary will be performed for the SAF. All medical history information will be listed.

[figure not shown]
#### 7.5 Protocol Deviations

All major protocol deviations will be summarized by deviation category and treatment group. This analysis will be performed for the Randomized set.

# 7.6 Lung function testing

[figure not shown]
The results of the spirometry measurements (including reversibility testing) at Screening Visit 1b will be listed for each subject including the FEV1, FVC (absolute values and percentage of

predicted values rounded to whole numbers). For the reversibility testing, both the absolute measurements and percentage change after inhaled bronchodilator will be presented. Spirometry data from the vendor may include several attempts for each subject/visit/timepoint with the best attempt flagged. If Screening Visit 1b is repeated, only the data from the repeat visit will be used in analysis. The results will be summarized by treatment and parameter for the mITT set and PPS. 7.7 **Efficacy Analyses** 7.7.1 **Analysis of Equivalence and Superiority** 7.7.1.1 **Calculation of the Primary Endpoints** Acceptability criteria. FEV1 baseline. The FEV1 baseline will be defined as the average of the acceptable pre-dose FEV1 values obtained at Visit 2 Randomization. If some of these measurements are missing or are not acceptable, the average will be calculated using the available measurements, however, a minimum of two pre-dose FEV1 values is required; subjects who have only one or no predose FEV1 measurements on Visit 2 Randomization will have their FEV1 baseline missing, and thus the subject will be excluded from analysis. Calculation of Change in Pre-Dose FEV1 From Baseline to Week 4. The endpoint of change in morning pre-dose FEV1 from the time of treatment randomization to Week 4 will be calculated as

# 7.7.1.3 Analysis of bioequivalence of test and reference treatments

To show the bioequivalence, the following steps will be taken:

[figure not shown]

2. Bioequivalence will be declared if the 90% confidence interval for the test/reference LS mean ratio is entirely contained within the interval from 80% to 125%.

Analysis of bioequivalence will be performed on the PPS.

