# 7.7.1.4 Analysis of superiority to placebo

The analysis of superiority will be performed separately for the Test treatment versus the Placebo and for the Reference treatment versus the Placebo. Each of these analyses will be performed as follows:

2. Superiority will be declared if the Test and Reference LS means are each greater than the Placebo LS mean and the respective p-values are < 0.05.

Analysis of superiority will be performed on the mITT set.

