### 7.8.7 Exposure to Product

The subjects will be instructed to use the diary to document all doses taken.

Study drug compliance will be determined separately for Run-In and Treatment period as

•	
	•
•	Planned number of doses is determined as follows:
	Training named of desces is determined as follows.
	$\circ$

Note that if Screening Visit 1b is repeated for reversibility assessment, then the date of the repeat visit will be used in the calculation of the planned number of doses for the run-in period.

All doses in the diary recorded on or after the date of Visit 2 and dosing time as reported in the spirometry data will be considered as belonging to the Treatment period. All doses in the diary prior to that date and time will be considered as belonging to the Run-in period.

Compliance will be rounded to whole percentages. The compliance will be analyzed using the descriptive statistics by study period and treatment group. The proportion of subjects with at least 70% compliance in the Run-In period and 75% to 125% compliance in the Treatment period will be tabulated for each study period and treatment group.

Date Oct 22, 2019

Duration of exposure will be calculated by study period as [Date of last use of study medication

in the period] – [Date of first use of study medication in the period] + 1. Duration of exposure

will be summarized descriptively by study period and treatment group.

Compliance and duration of exposure will also be listed.

These analyses will be performed for the SAF for the Run-in and Treatment periods and also

for the Run-in Failure Set for the Run-in period only.

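### Is it a fault that the SAP plans the test/reference ratio and its 90% CI only in the Per-protocol Set?

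*SAP*

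**What the plan says.** The equivalence decision appears in three places, and they agree.

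- Section 5 (Hypothesis of Equivalence) sets "A two-sided, 90% confidence interval on the test/reference ratio for the primary endpoint" and requires that it "is contained within the interval [80.00%, 125.00%] for the Per-protocol Set".
- Section 6.7 calls the PPS definitive for bioequivalence. It takes mITT subjects "who had between 75% and 125% compliance with the dosing schedule in the Treatment period, and had no major protocol deviations" judged to affect the primary endpoint, and fixes the set at the blinded data review meeting, before lock and unblinding.
- Section 7.7.1.3 closes with "Analysis of bioequivalence will be performed on the PPS".

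The superiority decision is equally consistent. Section 5 (Hypothesis of Superiority) assigns it to the mITT set. Section 6.6 says of that set: "This population will be considered as definitive for testing superiority". Section 7.7.1.4 says: "Analysis of superiority will be performed on the mITT set", with Test and Reference each compared with placebo in a separate analysis.

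On who leaves the PPS, Section 7.2 counts subjects in the SAF, mITT set and PPS. Section 7.1 makes treatment columns or strata the general rule for summary tables. Section 7.3 gives baseline tables for all three sets. Section 7.5 states: "All major protocol deviations will be summarized by deviation category and treatment group". Section 7.8.7 plans that the proportion of subjects with "75% to 125% compliance in the Treatment period will be tabulated for each study period and treatment group".

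**The concern.** Test versus Reference is the primary comparison, and its only visible estimate is in a set selected by what happened after randomization. Fixing that set blind prevents deliberate selection. It does not prevent compliance or deviations from differing between the two products. If they differ, and if excluded subjects respond differently, the PPS ratio can depart from the ratio in all treated randomized subjects.

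The planned tables do not measure that departure. Section 7.5 counts all major deviations, whereas Section 6.7 excludes only for those judged to matter to the endpoint. The baseline and compliance tables show who differs, not what the exclusions do to the ratio. The mITT analyses in 7.7.1.4 give each active arm against placebo and no test/reference interval. At stake would be an equivalence claim that holds in the PPS but would not hold in the mITT set.

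**Working it through.** **1. Is anything wrong or contradictory?** Set side by side, Sections 5, 6.7 and 7.7.1.3 name one set for equivalence, and Sections 5, 6.6 and 7.7.1.4 name one set for superiority. Each decision has one set, one criterion and no competing statement. A supportive mITT ratio would change neither set and would leave the 80% to 125% rule alone.

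**2. Can absence be inferred from this text?** Section 7.7.1.2 is not visible. Step 1 is missing from both 7.7.1.3 and 7.7.1.4. Section 5 breaks off in its description of the model, and the mITT definition in 6.6 appears to have a gap. LOCF is in the abbreviation list but nowhere in the remaining text, which suggests that missing-data wording was removed. Section 9 puts the table shells in a separate document, and Section 8 reports no change from a protocol that is not at hand. An mITT ratio could stand in any of these places.

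**3. How large could the effect be?** The visible SAP gives no sample size, SD, effect size or exclusion rate, so there is no figure to reproduce and every input below is assumed. Let p be the PPS ratio, xT and xR the shares excluded, and f the excluded subjects' mean change divided by their arm's PPS mean. Then

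mITT ratio = p × [(1 − xT) + xT·f] / [(1 − xR) + xR·f].

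With equal x and equal f the bracketed terms cancel and the ratio does not move. For p = 1.00:

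| Excluded, T v R | f = 0 | f = 0.5 |
|---|---|---|
| 10% v 10% | 1.000 | 1.000 |
| 15% v 10% | 0.85/0.90 = 0.944 | 0.925/0.95 = 0.974 |
| 20% v 10% | 0.80/0.90 = 0.889 | 0.90/0.95 = 0.947 |
| 25% v 5% | 0.75/0.95 = 0.789 | 0.875/0.975 = 0.897 |

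Only the last row with no response falls below 0.80. At 300 per arm, that imbalance is 0.20 / √(2 × 0.15 × 0.85 / 300) = 6.9 standard errors from equal exclusion.

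**4. Intervals.** Assume 300 randomized per arm, 15% v 10% excluded (255 and 270 in the PPS), Reference PPS mean 0.25 L and SD 0.25 L in both sets. Fieller limits are the roots θ of

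(mR² − z²·SD²/nR)θ² − 2·mT·mR·θ + (mT² − z²·SD²/nT) = 0, with z = 1.645.

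For the PPS at p = 0.95, mT = 0.2375 and mR = 0.25. The equation is 0.06187θ² − 0.11875θ + 0.05574 = 0, which gives 0.818 to 1.101. For the mITT set at f = 0.5, mT = 0.2375 × 0.925 = 0.2197 and mR = 0.25 × 0.95 = 0.2375, with 300 per arm. This gives 0.797 to 1.072.

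| 90% lower limit | PPS | mITT f = 0 | f = 0.5 | f = 0.75 | f = 0.9 |
|---|---|---|---|---|---|
| p = 1.00 | 86.5% | 80.9% | 84.3% | 85.9% | 86.8% |
| p = 0.95 | 81.8% | 76.4% | 79.7% | 81.2% | 82.1% |

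All upper limits are below 125%. At p = 1.00 both sets pass throughout. At p = 0.95 the mITT set fails only when f is below about 0.55, the value at which the same equation has its lower root at 0.80. At f = 0.9 the mITT lower limit is above that of the PPS, because the larger numbers outweigh the dilution. With 10% excluded in each arm and f = 0.5, the two lower limits at p = 0.95 are 82.05% (PPS) and 82.07% (mITT).

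**The case for a change.** The strongest reply is that the omission is real on the visible wording. The closing sentence of 7.7.1.3 names only the PPS, which makes a second set in the missing step less likely. The counts do not give a ratio. Dividing the active-arm means from the two superiority models is a poor substitute: in a simulation on assumed inputs, that quotient differed from a direct test/reference estimate by about ±0.05 with 100 per active arm and ±0.03 with 250, over the central 90% of trials. Harsher assumptions also move the ratio further. With a PPS ratio of 0.95, 20% v 10% excluded, no response in excluded Test subjects and full response in excluded Reference subjects, the mITT ratio is 0.95 × 0.80 / 1.00 = 0.760. The extra analysis would be cheap, and more credible if planned before unblinding.

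What stands is that no visible sentence plans an mITT ratio and that such a ratio would be informative. It does not follow that the plan is defective. Low response in every excluded subject is not implied by Section 6.7, which also removes subjects above 125% compliance, subjects just under 75%, and deviations that need not reduce response. The imbalance that drives the effect would show in the set counts and the by-arm compliance and deviation tables. Nor would an mITT ratio isolate the effect of exclusion. Under Section 3.1 an early-termination visit has at most one spirometry session, at the investigator's discretion, and Section 7.7.1.1 drops subjects without a baseline. The mITT ratio would therefore also depend on a missing-data rule that cannot be seen here.

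**Conclusion.** The concern does not hold. The SAP gives equivalence to a PPS fixed blind and superiority to the mITT set, consistently wherever it addresses either. It contains no wrong figure, contradiction or faulty rule on this point. What remains is a preference for a further supportive analysis, and removed text means one cannot say that it is absent.

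A changed conclusion needs several conditions at once: a PPS result near the limit, unequal exclusion and a clearly weaker response in excluded subjects. In the worked case (PPS ratio 0.95, 15% v 10% excluded, 300 per arm, mean and SD both 0.25 L), the mITT lower limit is 79.7% at half response and 81.2% at three quarters. All of these inputs are assumptions, so the figures show what is possible and say nothing about what this trial would find.
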